### C. Exit criteria

- (1) An allergic reaction occurs.
- (2) The patient requests withdrawal: at his or her own discretion or at the request of his or her legal representative. Subjects may refuse to participate in further studies at any time without providing reasons. Subjects will not be affected because of such decision.
- (3) Subjects are required to withdraw from the study in certain special circumstances. (eg, there is significant issues of compliance, safety, or surgery for venous malformations)
- (4) Other situations in which the study must be terminated. For example, the

investigators believe that continuing the study may be harmful to the health of subjects.

### D. Rejection criteria

- (1) Patients who violate the requirements of the test protocol
- (2) Patients with poor-recording, incomplete, or inaccurate data

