# III. Research design

- 1. This study is a prospective, nonrandomized, open-label, single-arm clinical trial. The sirolimus capsule (Rapamycin, Yixinke®), 0.5 mg/grain\*20/box, is produced by North China Pharmaceutical Co., Ltd.
- 2. All patients who meet inclusion criteria and sign informed consents receive sirolimus treatment for at least 6 months. Patients are followed up remotely in a regular schedule.
- 3. No less than 10 patients should be enrolled.

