### V. Therapeutic schedule

### A. Enrollment

Before starting the study, the investigator clearly and colloquially explains the study and its potential risks and benefits to the patient or his/her authorizer. Patient or his/her authorizer and the investigator sign and date the informed consent form. Only after signing the informed consent form can patient or his/her authorizer enter the screening section and then participate in the study. Patients who sign a written informed consent need to be assessed to determine if the patient meets the study criteria:

1) Demographic data and medical history of the patient;

2) vital signs;

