#### C. Adults' dosage regimen

1) Initial dose and dosing schedule: sirolimus 2mg, once a day. Maintain drug trough concentration of 5-10ng / mL in blood. If adverse events are too severe to tolerate, daily dosage can be reduced by 0.5mg every week. The minimum dosage is 1 mg/day. If patient still cannot tolerate minimum dosage, withdraw from the study. If patient could tolerate the possible adverse events, continue to take the original dose for 3 months, and evaluate improvement of disease condition.

2) Subsequent dose and dosing schedule: After taking sirolimus 2 mg once a day for 3 months, those with improved condition continue to take the original dose. If improvement of disease condition is not obvious, change dosage to 2.5mg-3mg once a day. If this dosage cannot be tolerated, patients may withdraw from the study. If it can be tolerated, continue to take sirolimus for another 3 months and reassess the improvement of condition.

3) Blood drug concentration test: Blood samples are taken at 1st month, 3rd months, and 6th months of dosage schedules.

4) Iron supplementation: For subjects with hemoglobin  $\leq 10.9$  g / dl, iron supplementation should be provided according to the standard dosing regimen, but iron supplementation is not considered as study treatment and will be recorded as concomitant medication.

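### Section IV.D rejects patients for protocol violation or poor data without saying from what, and Section VIII names no all-treated set, so treated patients could be left out of the analysis

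*Combined protocol and SAP*

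**What the plan says.** Section IV.D has two lines. It rejects "Patients who violate the requirements of the test protocol" and "Patients with poor-recording, incomplete, or inaccurate data". It gives no object for the rejection (enrolment, treatment or analysis), no threshold, no timing and no decision-maker.

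IV.D sits under the heading for selection of subjects, but as its own list. Exclusion is in IV.B. Exit is in IV.C, which covers withdrawal where "there is significant issues of compliance, safety, or surgery for venous malformations".

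Section III describes the design: "This study is a prospective, nonrandomized, open-label, single-arm clinical trial". On size it says only: "No less than 10 patients should be enrolled".

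Section VIII names the software, descriptive statistics, 95% confidence intervals and the topics to be analysed. It promises counts and percentages but names no analysis set, no denominator and no rule for missing data or withdrawals. Section VII asks for the incidence of adverse events and adverse reactions, also without a denominator.

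**The concern.** A rejection rule that is not tied to a stage of the trial can be applied after treatment has started, when the patient's course is known to the investigator. There is no blinding and no control arm, so the summary of treated patients is the whole result. With as few as 10 patients, each one carries a tenth of that result.

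If IV.D is used to drop treated patients, and those dropped differ in outcome from those kept, the reported efficacy and adverse-reaction figures describe a selected subgroup. The shift can go either way. Losing patients who did poorly makes the drug look better; losing patients who did well, for example over gaps in a diary, makes it look worse. Nothing in the plan requires the results of rejected patients to be shown, so a reader of the report could not tell which had occurred.

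**Working it through.** **1. Text check: what does rejection apply to?**

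| Place | Bearing on the question |
|---|---|
| IV heading | Selection of subjects, which allows a screening reading |
| V.A and VI.A | "Only after signing the informed consent form can patient or his/her authorizer enter the screening section and then participate in the study"; a four-week work-up precedes treatment. Some incomplete data could therefore arise before dosing |
| IV.B and IV.C | Exclusion and exit have their own lists, so IV.D should do something they do not |
| VI.B and VI.C | Evaluations at months 3 and 6, at end of therapy, and 6 and 12 months later, plus a diary kept throughout. Most data arise after the first dose |
| III | Says who is treated, not who is analysed |
| VIII | No set or denominator that would keep a rejected patient in |

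Removal after entry is the likely reading. It is not stated anywhere.

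**2. The plan's own figure.** The only number is the minimum of 10. No response rate, effect size, power or dropout is given, so there is nothing to reproduce. Everything below is illustration: the counts and rates are assumed, and the plan defines no responder endpoint.

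**3. Improved proportion, 4 of 10 improved.** With k patients rejected, the result is 4/(10 − k) if all are non-improvers and (4 − k)/(10 − k) if all are improvers. Intervals are exact (Clopper-Pearson) 95%.

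| k | Only non-improvers rejected | Only improvers rejected |
|---|---|---|
| 0 | 4/10 = 40% (12–74%) | 4/10 = 40% (12–74%) |
| 1 | 4/9 = 44% (14–79%) | 3/9 = 33% (7–70%) |
| 2 | 4/8 = 50% (16–84%) | 2/8 = 25% (3–65%) |
| 3 | 4/7 = 57% (18–90%) | 1/7 = 14% (0.4–58%) |

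With 8 of 20 improved, three rejections give at most 8/17 = 47% and at least 5/17 = 29%.

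**4. How extreme are those ends?** If three of the 10 are rejected without regard to outcome, there are C(10,3) = 120 equally likely choices. The result is 4/7 in 20 of them (17%), 3/7 in 60 (50%), 2/7 in 36 (30%) and 1/7 in 4 (3%). The expected result is 40%. The ends of the table need rejection to fall wholly on one outcome group.

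**5. Partial dependence on outcome.** Let p be the true improved share, r the rejected share of improvers and q that of non-improvers. The expected reported share is p(1 − r) / [p(1 − r) + (1 − p)(1 − q)]. Take p = 0.40.
- r = 0.05, q = 0.10 to 0.40: 0.38/0.92 = 41% to 0.38/0.74 = 51%.
- q = 0.05, r = 0.10 to 0.40: 0.36/0.93 = 39% to 0.24/0.81 = 30%.
- r = q: 40%.

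**6. Continuous polyp measures.** Removing k of n patients whose mean is R from an all-treated mean M gives M + [k/(n − k)](M − R). Take n = 10, M = 20% reduction and k = 1, 2, 3. With R = 0 the results are 22%, 25%, 29%. With R = 40% they are 18%, 15%, 11%.

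**7. Adverse reactions, 5 of 10.** Rejecting 1, 2 or 3 patients with a reaction gives 4/9 = 44%, 3/8 = 38%, 2/7 = 29%. Rejecting 1, 2 or 3 without one gives 5/9 = 56%, 5/8 = 63%, 5/7 = 71%.

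**8. Chance that the rule is met at all.** If each patient has an assumed 5%, 10%, 20% or 30% chance of meeting a criterion, 1 − (1 − chance)^10 gives 40%, 65%, 89% or 97% for at least one in 10.

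**The case against.** The strongest reply is that the consequence is inferred. No section links IV.D to Section VIII, and the heading above IV.D permits a screening reading. That stands as far as certainty goes: the documents support a likely effect, not a stated one. It does not remove the need for a sentence, because either reading leaves the text unclear.

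A reader might also infer several stronger things that the documents do not support.

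- *That patients who stop for intolerance would be rejected as protocol violators.* Section V.C itself provides that route ("If patient still cannot tolerate minimum dosage, withdraw from the study"), so following it is not a violation. Withdrawal does not by itself trigger IV.D.
- *That rejection is built to depend on outcome.* One adult withdrawal route opens only "If improvement of disease condition is not obvious" at month 3. To reach a biased result, the patient must then fail to tolerate the changed dose, choose to withdraw, be labelled incomplete, and be dropped from analysis. This is a possibility only.
- *That nobody could establish what happened.* Evaluations are scheduled through end of therapy, adverse events go into the case report form, and Section XII preserves all study data. The comparison could be made. What is missing is a requirement to report it.
- *That safety data are unprotected.* Sections VI.B and VII require events to be monitored, recorded, followed and their incidence reported. Only the denominator is open.

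The diary review at every visit is also a safeguard against incomplete records, and the diary tracks drug intake, not efficacy. Finally, the study is descriptive and the intervals overlap widely, so no test result is at stake.

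**Conclusion.** The point holds as an ambiguity with a likely and avoidable consequence. It is certain that IV.D has no object and that Section VIII has no all-treated set or denominator. It is likely, not certain, that IV.D would remove treated patients from the analysis.

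The possible shift is large for a trial of this size. At the floor of 10 patients, three removals could move an assumed 40% improved to anywhere between 14% and 57%, and an assumed 50% adverse-reaction rate to anywhere between 29% and 71%. These are worst cases on assumed counts, and they narrow as enrolment rises. The direction cannot be derived from the documents, so a claim that the plan overstates efficacy would go too far.

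This should be fixed. Confidence is medium, because the gap is plain but its use is not.

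**What to change.** In IV.D, state what patients are rejected from, and that rejection after the first dose does not remove a patient from the main analyses.

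In Section VIII, add:

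1. All patients who took at least one dose form the main efficacy and safety set, and are the denominator for adverse-event incidence.
2. All available post-baseline evaluations are used, with the number of patients shown at each visit. For continuous polyp measures, state how many treated patients have no post-baseline value. In any improved/not-improved summary, keep every treated patient in the denominator and show those without a post-baseline evaluation as a separate category.
3. IV.D exclusions are applied only in a supportive analysis.
4. Each rejected or withdrawn patient is listed with reason, time and available results.

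The cost is wording and a little more analysis. No new visits are needed, since the evaluations and event records are already planned in Sections VI and VII. Available evaluations will differ in treatment duration, which is why results are shown by visit. The reported figures may become less favourable.

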### V. Therapeutic schedule

### A. Enrollment

Before starting the study, the investigator clearly and colloquially explains the study and its potential risks and benefits to the patient or his/her authorizer. Patient or his/her authorizer and the investigator sign and date the informed consent form. Only after signing the informed consent form can patient or his/her authorizer enter the screening section and then participate in the study. Patients who sign a written informed consent need to be assessed to determine if the patient meets the study criteria:

1) Demographic data and medical history of the patient;

2) vital signs;

### B. Children's dosage regimen

Oral administration

The initial dose of oral rapamycin intake is  $1 \text{ mg/m}^2$  of body surface area. Drug trough concentration in patient's blood is maintained at 5-10 ng/ml.

#### C. Adults' dosage regimen

1) Initial dose and dosing schedule: sirolimus 2mg, once a day. Maintain drug trough concentration of 5-10ng / mL in blood. If adverse events are too severe to tolerate, daily dosage can be reduced by 0.5mg every week. The minimum dosage is 1 mg/day. If patient still cannot tolerate minimum dosage, withdraw from the study. If patient could tolerate the possible adverse events, continue to take the original dose for 3 months, and evaluate improvement of disease condition.

2) Subsequent dose and dosing schedule: After taking sirolimus 2 mg once a day for 3 months, those with improved condition continue to take the original dose. If improvement of disease condition is not obvious, change dosage to 2.5mg-3mg once a day. If this dosage cannot be tolerated, patients may withdraw from the study. If it can be tolerated, continue to take sirolimus for another 3 months and reassess the improvement of condition.

3) Blood drug concentration test: Blood samples are taken at 1st month, 3rd months, and 6th months of dosage schedules.

4) Iron supplementation: For subjects with hemoglobin  $\leq 10.9$  g / dl, iron supplementation should be provided according to the standard dosing regimen, but iron supplementation is not considered as study treatment and will be recorded as concomitant medication.

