### C. Degree of adverse reactions:

- 1) Mild: causing mild discomfort which can be tolerated and does not affect daily life; under this circumstance, the subject does not need to discontinue medication.
- 2) Moderate: causing discomfort which affects patients' daily life.
- 3) Severe: affecting daily life; cannot be endured by the subject or cause organ damage and need to withdraw medication.
- 4) Very serious: risk of disability or death; require emergent rescue and drug withdrawal.

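### For adults, V.C allows stepwise dose reduction for an intolerable adverse event while VII.C attaches drug withdrawal to it, and no section says which governs

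*Combined protocol and SAP*

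**What the plan says.** Two sections of the combined protocol and SAP attach a drug action to an adverse event.

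**V.C, Adults' dosage regimen, item 1.** The starting point is "Initial dose and dosing schedule: sirolimus 2mg, once a day". For an intolerable event, "If adverse events are too severe to tolerate, daily dosage can be reduced by 0.5mg every week". The floor follows: "The minimum dosage is 1 mg/day". Withdrawal comes last: "If patient still cannot tolerate minimum dosage, withdraw from the study". Where the event is tolerated, the instruction is "If patient could tolerate the possible adverse events, continue to take the original dose for 3 months".

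**V.C, item 2.** At the higher dose used after month 3, the text is "If this dosage cannot be tolerated, patients may withdraw from the study". No step-down is mentioned there.

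**VII.C, Degree of adverse reactions.** The mild grade says that the drug need not be stopped. The moderate grade names no drug action. The severe grade covers a reaction that affects daily life and "cannot be endured by the subject or cause organ damage and need to withdraw medication". The very serious grade is "risk of disability or death; require emergent rescue and drug withdrawal".

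Three other sections bear on the point. VII.D counts an event as an adverse reaction in the top three of its five relatedness categories, the lowest of which is possible relation. Exit criterion (3) in IV.C requires a patient to leave in special circumstances, with significant safety issues among its examples. Exit criterion (4) rests on the investigator's belief that continuing may be harmful. VII.F asks for immediate protective measures without naming a drug action.

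**The concern.** The triggers in V.C item 1 and VII.C item 3 mean the same thing: an event that the patient cannot bear. The attached actions differ. V.C offers gradual reduction, with withdrawal at the end of it; VII.C says that the medication needs to be withdrawn. Two investigators who each follow the protocol could therefore keep one patient on drug and stop it in another with the same event.

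This matters because safety is one of the two objectives in section II, and section XI states that the drug is used outside its indication. The ambiguity also reaches the safety data. If withdrawal is part of what makes a reaction severe, the recorded grade depends on the investigator's action as well as on the reaction.

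**Working it through.** The protocol derives no figure on this point, so there is none to reproduce. The check compares the texts and adds one small illustration.

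**Step 1. Do both texts reach the same patients?** V.C speaks of adverse events and covers adults only; the children's section (V.B) gives no rule for adverse events. VII.C grades adverse reactions, which are the causally related subset. Under VII.D, possible relation is enough. Both texts therefore apply to an adult whose event is judged at least possibly related to sirolimus.

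**Step 2. Do the actions differ?**

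| Event in an adult | V.C item 1 | VII.C |
|---|---|---|
| Cannot be tolerated | May be reduced weekly; withdrawal if the minimum is not tolerated | Severe: withdrawal needed |
| Organ damage without symptoms | Not mentioned; tolerance is the only criterion | Severe: withdrawal needed |

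The first row is a direct conflict of wording. The second is an inference from what V.C leaves out. It could arise in practice, because VI.B repeats the baseline examinations at months 3 and 6, and these include liver and kidney function (VI.A).

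**Step 3. Does another section rank the two texts?** No. Exit criteria (3) and (4) and VII.F are general. None names a drug action by type of event or refers to V.C or VII.C.

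**Step 4. What if VII.C is read as a grading scale only?** Withdrawal then becomes part of the definition of severe. An unendurable reaction managed by dose reduction does not fully meet that definition, and the moderate grade describes only discomfort that affects daily life. Such a reaction has no clear grade.

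**Step 5. Illustration of the difference.** Inputs from V.C item 1: start 2 mg/day, step 0.5 mg per week, floor 1 mg/day. Assumptions: the event persists at every step, each reduced dose lasts one week, and no exit criterion is invoked.

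- Number of reductions: (2 − 1) / 0.5 = 2, that is 2 → 1.5 → 1 mg/day.
- First cut immediate: 2 × 7 = 14 further days; 7 × 1.5 + 7 × 1.0 = 10.5 + 7 = 17.5 mg.
- First cut after another week at 2 mg: 3 × 7 = 21 further days; 7 × 2 + 17.5 = 14 + 17.5 = 31.5 mg.
- Withdrawal under VII.C: 0 further days and 0 mg.

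V.C does not say when the first cut is made, so both cases are shown. If the event becomes tolerable at a reduced dose, V.C gives no reason to withdraw at all, and the illustration does not cover that patient.

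**The case against.** The best defence is that VII.C is a severity scale, placed in the chapter on recording and reporting, and that its moderate grade names no drug action, as a treatment algorithm would have to. That reading is open. It moves the problem without removing it, because the grade of an unendurable reaction then turns on what the investigator did (step 4).

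The second defence is that V.C is permissive: the dose can be reduced, so stopping at once satisfies both texts. This stands. A reader might infer that anyone handled under one section has breached the other and so faces rejection under IV.D. The documents do not support that. Immediate withdrawal breaches neither text, and IV.D does not mention this situation.

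The third is that exit criterion (3) is mandatory and plausibly covers many serious cases. That is fair, and it narrows the practical gap. It is still too general to tell an investigator whether an intolerable event calls for a step-down or for withdrawal.

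Two stronger readings also fail.

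- A reader might infer that a patient with organ damage would be held at full dose for up to 3 months. V.C does not say so and does not define tolerance as the absence of symptoms. VI.B provides weekly checks in the first month and regular safety monitoring throughout, and the exit criteria and VII.F remain available.
- A reader might infer that a main tolerability endpoint is compromised. The plan defines no discontinuation endpoint. VII.D, VII.E and VIII.B call for the incidence of adverse events and reactions and their relation to the drug.

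**Conclusion.** The conflict is real and stands in the current text. It is limited to adults and to events judged at least possibly related to sirolimus. For an intolerable event, V.C permits a step-down, VII.C calls for withdrawal, and nothing ranks them, so patients with the same event may be handled differently. On the assumptions of the illustration, the difference is about 14 to 21 further days on drug against none. The organ-damage gap is secondary, because it is inferred from the silence of V.C. The alternative reading of VII.C leaves a grading defect in place of the conflict.

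The point deserves correction because it concerns patient safety and costs little to resolve. It does not show that any planned result is biased, and it implies nothing about which rule is clinically right.

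**What to change.** Amend the protocol in three places.

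1. Reconcile V.C item 1 with VII.C so that each type of event (intolerable, organ-damaging, very serious) has one stated drug action in one place. State explicitly what applies to organ damage found without symptoms.
2. Cross-refer that text to exit criteria (3) and (4) in IV.C, so that their relation to the dosing rule is clear.
3. Define the VII.C grades by the features of the reaction alone, without reference to the drug action taken. VII.E already requires treatment measures to be recorded in the case report form, so the action can be captured there, separately from the grade.

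The investigators choose the clinical rule. The cost is a short amendment, with no added visits, tests or patients.

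### The month-3 dose increase for adults is not tied to the trough target, names only withdrawal for intolerance, and leaves room for patients without obvious improvement to drop out of the analysis

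*Combined protocol and SAP*

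**What the plan says.** All references are to the combined protocol and SAP.

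- **Trough target.** V.C item 1 starts adults on 2 mg daily and instructs: "Maintain drug trough concentration of 5-10ng / mL in blood". It allows weekly 0.5 mg reductions for intolerable adverse events, down to 1 mg/day, and then: "If patient still cannot tolerate minimum dosage, withdraw from the study".
- **Month-3 rule.** V.C item 2 splits patients by response. For improvers: "After taking sirolimus 2 mg once a day for 3 months, those with improved condition continue to take the original dose". For the rest: "If improvement of disease condition is not obvious, change dosage to 2.5mg-3mg once a day". On intolerance of the raised dose: "If this dosage cannot be tolerated, patients may withdraw from the study". Item 2 does not mention the trough or a step back to 2 mg.
- **Sampling.** V.C item 3: "Blood samples are taken at 1st month, 3rd months, and 6th months of dosage schedules".
- **Evaluations.** III item 2 plans at least 6 months of treatment. VI.B evaluates efficacy at months 3 and 6. VI.C adds an evaluation when drug therapy ends, but does not say that it applies to patients who withdraw early.
- **Who is analysed.** IV.D(2) lists for rejection: "Patients with poor-recording, incomplete, or inaccurate data". VIII names no analysis set, no rule for withdrawals and no handling of missing data. III item 3 sets a minimum of 10 patients, in a single arm.

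**The concern.** Two instructions can meet in the same patient. An adult whose month-3 trough is high in the target range, and whose disease has not obviously improved, is to be raised under item 2 and kept at or below 10 ng/mL under item 1. The protocol does not say which prevails. At stake is exposure above the protocol's own ceiling.

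The exit that follows is selective. Improvers stay on 2 mg, so only patients judged not obviously improved can leave because 2.5-3 mg was not tolerated. Each of them has just taken 2 mg for three months, so a lower dose of known tolerability exists, yet item 2 provides no return to it. A patient who stops between months 3 and 6 may lack the month-6 evaluation and so have incomplete data. If such patients are then rejected, the improved share among those left is higher than among those treated. There is no control arm in which a similar loss could offset this.

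**Working it through.** The plan states no figure to reproduce here: III item 3 gives a minimum of 10 with no design inputs, and no responder rate is defined. Both calculations below are therefore illustrations.

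**1. Dose step against the trough ceiling**

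Inputs from V.C: 2 mg starting dose, 2.5 or 3 mg raised dose, target 5-10 ng/mL. Assumption, not in the documents: steady trough is proportional to dose.

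- Dose rise: 2.5/2 − 1 = 25%; 3/2 − 1 = 50%.
- Highest month-3 trough T that stays at or below 10 ng/mL after the increase: T = 10/(new dose/2).
  - 2.5 mg: 10/1.25 = 8.0 ng/mL.
  - 3 mg: 10/1.5 = 6.7 ng/mL.
- Where a patient within 5-10 ng/mL at month 3 would land:
  - 2.5 mg: 5 × 1.25 = 6.25 to 10 × 1.25 = 12.5 ng/mL.
  - 3 mg: 5 × 1.5 = 7.5 to 10 × 1.5 = 15 ng/mL.

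So part of the on-target range would overshoot with either step. The documents give no trough distribution, so the share of patients affected cannot be computed.

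**2. When the overshoot would be seen**

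If item 3 counts from the start of treatment, the level after a month-3 increase is drawn at month 6, three months later. If it counts from the start of each schedule (items 1 and 2 are each headed as a dosing schedule, and item 3 uses the plural), a level falls one month after the increase. The text supports either reading.

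**3. Leaving out patients who stop after the increase**

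Assumed: 10 treated, x improved, w patients without obvious improvement rejected. Improved share = x/(10 − w).

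| x | w = 0 | w = 1 | w = 2 |
|---|---|---|---|
| 3 | 30.0% | 3/9 = 33.3% (+3.3) | 3/8 = 37.5% (+7.5) |
| 5 | 50.0% | 5/9 = 55.6% (+5.6) | 5/8 = 62.5% (+12.5) |
| 7 | 70.0% | 7/9 = 77.8% (+7.8) | 7/8 = 87.5% (+17.5) |

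For scale, the exact (Clopper-Pearson) 95% interval for 5/10 is 18.7-81.3%, a half-width of (81.3 − 18.7)/2 = 31.3 points. Every shift in the table is smaller than that. For this exit, however, the shift is always upward, and the 95% interval planned in VIII.A would not reflect it.

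**4. Other exits**

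Intolerance at 1 mg (item 1) and the exits in IV.C ("Subjects are required to withdraw from the study in certain special circumstances", for example) can remove improvers as well. No net direction can be derived for them. Nor can one be derived for continuous measures such as polyp size and load: a patient without obvious improvement may still have some reduction.

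**The case against.** The strongest reply is that the items should be read together. The trough instruction in item 1 reads naturally as a standing one, and V.B gives children the same target with no time limit. A trough is already due at month 3, when the dose decision is made, and the 2.5-3 mg range leaves the investigator a choice. On this reading only a cross-reference is missing, and item 3 may already provide a level one month after the increase. This stands in part. A reader might infer that item 2 overrides the target, or that patients will be taken above 10 ng/mL; the documents say neither. They leave the order of precedence open, and they leave open when the next level is drawn.

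On the analysis, the route is long. The patient must be raised, be intolerant, take a permissive exit, miss the end-of-therapy evaluation, be judged incomplete despite a month-3 evaluation, and then be rejected. Item 2 does not forbid using item 1's step-down instead. That too is fair. A reader might infer that the plan orders the exclusion of these patients, or that all early exits favour the drug. Neither follows: IV.D(2) permits rejection without saying that stopping early makes data incomplete, and the other exits have no fixed direction. The objection does not remove the fact that nothing in IV.D or VIII keeps a treated patient in the analysis.

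It is also fair that scoring every early stopper as not improved would override a measured end-of-therapy result and could bias against the drug. The change proposed below avoids that.

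**Conclusion.** The point holds as a gap in stated rules that is cheap to close; it does not show that any stated figure is wrong. Item 2 orders a 25-50% increase without reference to the trough target and names only withdrawal for intolerance. Under dose proportionality, overshoot starts from month-3 troughs above 8.0 ng/mL (2.5 mg) or 6.7 ng/mL (3 mg), with unknown frequency.

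If patients leaving by the item 2 exit are rejected, an improved/not improved summary shifts upward: by about 3 to 8 points for one patient in ten and 8 to 18 points for two, with 3 to 7 of 10 improved. These counts are assumed and the shifts lie within sampling error. The upward direction applies to this exit and to that kind of summary only. Confidence is medium, because the practical effect depends on how often patients have high troughs and how often they stop after the increase, and the documents inform neither.

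**What to change.** 1. **V.C items 2 and 3.** State that the 5-10 ng/mL range limits the response-driven increase, judged from the month-3 trough already drawn. State that the item 3 sampling times restart at the increase, so that a level is taken about 1 month later.
2. **V.C item 2.** For intolerance at 2.5-3 mg, return to the previously tolerated 2 mg before withdrawal is considered.
3. **IV.D and VIII.B.** Keep every patient who received sirolimus in the efficacy and safety analysis, whatever the reason for stopping. Carry out the VI.C end-of-therapy evaluation for those who stop early. Report their last measured values and the number missing at month 6. In any improved/not improved summary, keep them in the denominator, and count as not improved those without a post-stop evaluation showing improvement.

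Cost: a few sentences in these sections, and within the 6-month plan at most one extra blood sample per raised patient (none if item 3 already restarts). The month-6 figure may be slightly less favourable, and some patients without obvious improvement but with a high trough would not receive the increase.
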